1.2.8 Clinical Experience

The combination of ETBX-011, ETBX-061, and ETBX-051 vaccine has not been tested in humans.

This Phase I study is the first clinical study of this vaccine combination in subjects with advanced cancer.

1.2.9 Rationale

The preclinical data with the combination ETBX-011, ETBX-061, and ETBX-051 vaccine support this Phase I study to evaluate the safety, preliminary efficacy, and immunogenicity of the vaccine. Subsequent trials will involve the use of this vaccine in combination with checkpoint inhibitor monoclonal antibodies (MAbs) and other immune modulators.

2 ELIGIBILITY ASSESSMENT AND ENROLLMENT

2.1 ELIGIBILITY CRITERIA

2.1.1 Inclusion Criteria

- 2.1.1.1 Age \geq 18 years (male and female).
- 2.1.1.2 Ability to understand and provide signed informed consent that fulfills Institutional Review Board (IRB)'s guidelines.
- 2.1.1.3 Subjects with cytologically or histologically confirmed locally advanced or metastatic solid tumor malignancy.
- 2.1.1.4 Subjects must have completed or had disease progression on at least one prior line of disease-appropriate therapy or not be candidates for therapy of proven efficacy for their disease.
- 2.1.1.5 Subjects may have measurable or nonmeasurable but evaluable disease as defined in section 6.3.1. Subjects with surgically resected locally advanced or metastatic disease at high risk of relapse are also eligible.
- 2.1.1.6 Eastern Cooperative Oncology Group (ECOG) performance status \leq 1 ([Appendices](#)
- 2.1.1.7 [Appendix A](#))
- 2.1.1.8 Subjects who have received prior CEA, MUC1, and/or Brachyury-targeted immunotherapy (vaccine) are eligible for this trial if this treatment was discontinued at least 4 weeks prior to enrollment.
- 2.1.1.9 Resolution of clinically significant side effects of prior chemotherapy, radiotherapy, immunotherapy or surgical procedures to NCI CTCAE Grade \leq 1 or grade \leq 2 for neuropathy.
- 2.1.1.10 Adequate hematologic function at screening, as follows:
 - 2.1.1.10.1 Absolute neutrophil count (ANC) \geq 1 x 10⁹/L
 - 2.1.1.10.2 Hemoglobin \geq 9 g/dL
 - 2.1.1.10.3 Platelets \geq 75,000/mcL.

2.1.1.11 Adequate renal and hepatic function at screening, as follows:

2.1.1.11.1 Serum creatinine ≤ 1.5 x upper limit of normal (ULN) OR creatinine clearance (CrCl) ≥ 40 mL/min (if using the Cockcroft-Gault formula below):

i. *Female* CrCl = [(140 - age in years) x weight in kg x 0.85] / [72 x serum creatinine in mg/dL]

ii. *Male* CrCl = [(140 - age in years) x weight in kg x 1.00] / [72 x serum creatinine in mg/dL]

2.1.1.11.2 Bilirubin ≤ 1.5 x ULN OR in subjects with Gilbert's syndrome, a total bilirubin ≤ 3.0 x ULN

2.1.1.11.3 Alanine aminotransferase (ALT) and aspartate aminotransferase (AST) ≤ 2.5 x ULN, unless liver metastases are present, then values must be ≤ 3 x ULN)

2.1.1.12 The effects of the combination ETBX-011, ETBX-051, ETBX-061 vaccine regimen on the developing human fetus are unknown. For this reason, female subjects of childbearing potential defined as any female who has experienced menarche and who has not undergone surgical sterilization (hysterectomy or bilateral oophorectomy or tubal ligation) or who is not postmenopausal (menopause being defined clinically as 12 months of amenorrhea in a woman over 45 in the absence of other biological or physiological causes) and male patients who are not surgically sterile (vasectomy etc.), must agree to use acceptable contraceptive methods for the duration of the study and for one month after the last vaccination. Acceptable forms of contraception include oral contraceptives, intrauterine device, condom or vaginal diaphragm plus spermicidal (gel/foam/cream/vaginal suppository), or total abstinence.

2.1.1.13 Ability to attend required study visits and return for adequate follow up, as required by this protocol.

2.1.2 Exclusion Criteria

2.1.2.1 Pregnant and nursing women. Because there is an unknown but potential risk for adverse events in nursing infants secondary to treatment of the mother with combination ETBX-011, ETBX-051, ETBX-061, breastfeeding should be discontinued if the mother is treated with combination ETBX-011, ETBX-051, ETBX-061. These potential risks may also apply to other agents used in this study.

2.1.2.2 There should be a minimum of 4 weeks from any prior investigational drug, chemotherapy, immunotherapy, with the exception of hormonal therapy for prostate and breast cancers, HER2-directed therapy for HER2+ breast or stomach cancer (3+ IHC or FISH+), drugs targeting EGFR, ALK or ROS1 in EGFR, ALK, ROS1-mutated lung cancer, respectively, or standard maintenance therapies for any solid tumor under the condition that subjects are on these therapies for at least two months before start of trial treatment.

2.1.2.3 There should also be a minimum of 4 weeks from any prior radiotherapy except for palliative bone directed therapy.

2.1.2.4 Known active brain or central nervous system metastasis (less than 1 month out from definitive radiotherapy or surgery), or seizures requiring anticonvulsant treatment, or clinically significant cerebrovascular accident or transient ischemic attack (<3 months).

- 2.1.2.5 Subjects with active autoimmune disease requiring systemic immunosuppressive treatment within the past 4 weeks such as but not restricted to inflammatory bowel disease, systemic lupus erythematosus, ankylosing spondylitis, scleroderma, or multiple sclerosis. A history of autoimmune disease which is not active nor has required recent systemic immunosuppressive therapy (< 4 weeks prior to enrollment) is not reason for exclusion.
- 2.1.2.6 Subjects with serious intercurrent chronic or acute illness, such as cardiac or pulmonary disease, hepatic disease, or other illness considered by the Investigator as high risk for investigational drug treatment.
- 2.1.2.7 Subjects with clinically significant heart disease, such as congestive heart failure (class II, III, or IV defined by the New York Heart Association functional classification), history of unstable or poorly controlled angina, or history (< 1 year) of ventricular arrhythmia.
- 2.1.2.8 Subjects with a medical or psychological impediment that would impair the ability of the subject to receive therapy per protocol or impact ability to comply with the protocol or protocol-required visits and procedures.
- 2.1.2.9 History of second malignancy within 3 years prior to enrollment except for the following: adequately treated non-melanoma skin cancer, cervical carcinoma in situ, superficial bladder cancer or other localized malignancy after discussion with the medical monitor.
- 2.1.2.10 Presence of a known active acute or chronic infection, including human immunodeficiency virus (HIV, as determined by enzyme-linked immunosorbent assay [ELISA] and confirmed by western blot) and hepatitis B and hepatitis C virus (HBV/HCV, as determined by HBsAg and hepatitis C serology).
- 2.1.2.11 Subjects on systemic intravenous or oral corticosteroid therapy with the exception of physiologic doses of corticosteroids (\leq the equivalent of prednisone 10 mg/day) or other immunosuppressives such as azathioprine or cyclosporin A are excluded on the basis of potential immune suppression. For these subjects these excluded treatments must be discontinued at least 2 weeks prior to enrollment for recent short course use (\leq 14 days) or discontinued at least 4 weeks prior to enrollment for long term use ($>$ 14 days). In addition, the use of corticosteroids as premedication for contrast-enhanced studies is allowed prior to enrollment and on study.
- 2.1.2.12 Subjects with known allergy or hypersensitivity to any component of the investigational product will be excluded.
- 2.1.2.13 Subjects with acute or chronic skin disorders that will interfere with injection into the skin of the extremities or subsequent assessment of potential skin reactions will be excluded.
- 2.1.2.14 Subjects vaccinated with a live (attenuated) vaccine (e.g., FluMist[®]) or a killed (inactivated)/subunit vaccine (e.g., PNEUMOVAX[®], Fluzone[®]) within 28 days or 14 days, respectively, of the first planned dose of ETBX vaccine.

2.1.3 Recruitment Strategies

This study will be listed on available websites (www.clinicaltrials.gov, <https://ccr.cancer.gov/clinical-trials-search-start>) and participants will be recruited from the current patient population at NIH.

2.2 SCREENING EVALUATION

All screening tests and procedures must be performed within 28 days prior to the first planned dosing of the study drug, unless otherwise noted. The following procedures and evaluations will be performed and documented in the subject's source records.

- History and physical exam including ECOG performance status and vital signs
- 12-Lead ECG
- Clinical laboratory tests (within 16 days prior to drug administration)
 - Chemistry: sodium, potassium, chloride, bicarbonate, calcium, glucose, BUN, creatinine, ALT, AST, alkaline phosphatase, total protein, albumin, and total and direct bilirubin.
 - Hematology: complete blood count (CBC) with differential and platelets
 - Coagulation panel: PT, INR, and PTT.
 - Urinalysis.
- Serum pregnancy test (β -HCG) for females of childbearing-potential and women < 12 months since the onset of menopause (within 16 days prior to enrollment)
- HBV (HBsAg), HCV (anti-HCV), HIV (anti-HIV) screening (within 3 months prior to enrollment)
- Appropriate tumor imaging and assessment. All baseline tumor measurements should be performed based on the subject's qualifying scan obtained within 28 days prior to the start of treatment.
- Confirmation of diagnosis. A report from any CAP or CLIA certified laboratory is acceptable.

2.3 REGISTRATION PROCEDURES

Registration will be a two-part process as patients are screened on this protocol. Authorized staff must register an eligible candidate with NCI Central Registration Office (CRO) within 24 hours of signing consent. To initially register a subject after the participant has signed the consent, complete the top portion of the registration Eligibility Checklist from the website (<http://home.ccr.cancer.gov/intra/eligibility/welcome.htm>) indicating that the patient is being registered for screening and send via encrypted email to: NCI Central Registration Office [contact]. Once eligibility is confirmed after completion of screening studies, complete the remainder of the form which is the eligibility checklist, indicating that the patient is being registered for treatment and email the completed registration checklist to the CRO at NCI Central Registration Office [contact]. After confirmation of eligibility at Central Registration Office, CRO staff will call pharmacy to advise them of the acceptance of the patient on the protocol prior to the release of any investigational agents. Verification of Registration will be forwarded electronically via e-mail to the research team. A recorder is available during non-working hours.

Subjects that do not meet screening criteria should be removed from the study following the procedure in section 3.7.3.

2.3.1 Treatment Assignment Procedure

Cohorts

Number	Name	Description
1	Dose De-Escalation	Subjects enrolled to dose de-escalation cohorts
2	Dose Expansion	Subjects enrolled at the MTD after the MTD is established

Arms

Number	Name	Description
1	Dose De-Escalation	Combination ETBX-011, ETBX-051, ETBX-061 adenoviral vaccine regimen dose de-escalation
2	Dose Expansion	Combination ETBX-011, ETBX-051, ETBX-061 adenoviral vaccine regimen dose

Arm Assignment

Subjects in cohort 1 will be directly assigned to arm 1.
Subjects in cohort 2 will be directly assigned to arm 2.

2.4 BASELINE EVALUATION

All subjects are required to complete baseline evaluations within 1 day prior to the first planned dosing of the study drug (Any screening evaluation done on D-1 of treatment can also serve for the baseline evaluation). The following procedures and evaluations will be performed and documented in the subject's source records.

- History and physical exam including ECOG performance status and vital signs
- Serum pregnancy test (β -HCG) for females of childbearing-potential and women < 12 months since the onset of menopause.
- Chemistry: sodium, potassium, chloride, bicarbonate, calcium, glucose, BUN, creatinine, ALT, AST, alkaline phosphatase, total protein, albumin, and total and direct bilirubin.
- Hematology: CBC with differential and platelets

3 STUDY IMPLEMENTATION

3.1 STUDY DESIGN

This is a Phase I trial in subjects with advanced cancer.

The combination vaccine regimen is three different adenoviral vaccines (ETBX-011, ETBX -061 and ETBX-051), administered to patients at the same time. All utilize the same second generation E1(-), E2 (-) vector.

ETBX-011 is a CEA-targeting vaccine that comprises the Ad5 [E1-, E2b-] vector and a modified CEA (CEA(6D)) gene insert. The investigational product ETBX-061 is a MUC1-targeting vaccine

that comprises the Ad5 [E1-, E2b-] vector and a modified MUC1 (MUC1c) gene insert. The investigational product ETBX-051 is a Brachyury-targeting vaccine that comprises the Ad5 [E1-, E2b-] vector and a modified Brachyury gene insert. (Table 8).

3.1.1 Dose Limiting Toxicity

For the purposes of dose escalation a dose limiting toxicity (DLT) is defined as:

- Any Grade 3 or greater toxicity that is possibly related to the vaccine and as defined by Common Terminology Criteria for Adverse Events (CTCAE) Version 5.0 with the exception of transient (≤ 24 hours) Grade 3 flu-like symptoms or fever, which is controlled with medical management or transient (≤ 24 hours) Grade 3 fatigue, skin reactions or rash, headache, nausea, emesis that resolves to Grade ≤ 1 or asymptomatic grade 3 amylase/lipase elevation. For purposes of dose escalation the DLT evaluation period will be for 3 weeks following the first dose of drug.

Subjects experiencing a DLT will be removed from protocol therapy.

3.1.2 Dose De-Escalation

Up to six patients will be enrolled at dose level 1. If ≤ 1 of 6 patients experience a DLT, initiation of the dose expansion phase will occur. If ≥ 2 of 3 or 6 experience DLT in the initial dose level, then dose de-escalation will occur. Up to six patients will be enrolled at the lower dose level (-1) (1×10^{11} VP). If ≤ 1 of 6 patients experience a DLT, then the maximum tolerated (MTD) will be declared at this dose, and initiation of the dose expansion phase will occur. If ≥ 2 of 3 or 6 experience DLT at dose level -1, then an amendment may be written to evaluate a further dose de-escalation.

In the second part, dose expansion will occur when the MTD has been determined. An additional 4 subjects will be enrolled in the dose expansion component of the trial, for a total of 10 subjects treated at the MTD.

A schematic overview of the study is shown in Figure 6.

In the initial component of the study, 3 to 6 subjects will be sequentially enrolled starting at the standard dose at dose level 1. During enrollment at each dose level, there will be a minimum of 3 days between enrolling successive subjects. DLTs will be monitored continuously.

Dose levels are shown in Table 4. No intra-patient dose escalations are permitted.

Table 4: Dose Levels for Each ETBX VP

Dose Level (DL)	ETBX VP
Standard (1)	5×10^{11}
-1	1×10^{11}

[figure not shown]
Standard dose (DL 1) (5×10^{11} VP):

- If ≤ 1 of the initial 6 subjects experience a DLT, dose expansion will commence.
- If >1 of the initial 3 subjects, or if ≥ 2 of the 6 total subjects experience a DLT, enrollment at DL -1 will commence.

Dose de-escalation DL -1 (1×10^{11} VP):

- If ≤ 1 of the initial 6 subjects experience a DLT, this dose level will be defined as the MTD and dose expansion will commence.
- If >1 of the initial 3 subjects, or if ≥ 2 of the 6 total subjects experience a DLT, then a protocol amendment may be written to evaluate a further dose de-escalation..

Figure 6: Study Design and Treatment Schema

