3.2 ADMINISTRATION AND DURATION OF TREATMENT

Each of the three ETBX vaccines will be administered on Weeks 0, 3, and 6 followed by booster vaccines every 8 weeks for up to a year. Treatment may be shorter for patients who experience progressive disease (unequivocal or confirmed) or unacceptable toxicity, withdraw consent, or if the Investigator feels it is no longer in their best interest to continue treatment. For specifics on drug administration see section [11.1.5](#).

Vital sign assessments (temperature, heart rate, blood pressure, respiratory rate) are to be obtained after the subject has been in a seated resting position for at least 5 minutes. For the first injection, vital signs must be assessed 30 and 60 minutes after the injection. Vital signs must be assessed 30 minutes after the subsequent injections.

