3.5 STUDY CALENDAR

Assessment	Screening	Treatment (Every 3-Week Dosing)			Bimonthly_Boosters (Every 8-Week Dosing)						End of Treatment (within 90 days after the last vaccine) ^m	Follow Up ^l
		Baselin e/0	3	6	14	22	30	38	46	54		
Study Week	Day -28 to -1ⁿ											
Clinic Visit	X	X ^c	X	X	X	X	X	X	X	X	X	
Informed Consent	X ^a											
Inclusion/Exclusion	X											
Demographics	X											
Confirmation of diagnosis (path report)	X											
Physical Examination, Height ^b , Weight, ECOG	X ^c	X ^c	X	X	X	X	X	X	X	X	X	
Medical History ^d	X	X ^c										
Concomitant Medications	X	X ^c	X	X	X	X	X	X	X	X	X	
Vital Signs ^e	X	X ^c	X	X	X	X	X	X	X	X	X	
12-Lead ECG	X				X	X	X	X	X	X	X	
Confirm Contraceptive Measures ^f	X											
Study Drug Injection/ Injection Site Reaction Monitoring ^g		X	X	X	X	X	X	X	X	X	X	

Assessment	Screening	Treatment (Every 3-Week Dosing)			Bimonthly_Boosters (Every 8-Week Dosing)						End of Treatment (within 90 days after the last vaccine) ^m	Follow Up ^l
		Baseline e/0	3	6	14	22	30	38	46	54		
Study Week	Day -28 to -1ⁿ	Baseline e/0	3	6	14	22	30	38	46	54		
Dispensation of Subject Diary Card ^h		X										
Review of Subject Diary Card ^h			X									
Tumor Imaging ⁱ	X			X	X	X	X	X	X	X		
Pregnancy Test ^j	X ^{c,n}	X ^c	X	X	X	X	X	X	X	X	X	
Urinalysis	X ⁿ										X	
Chemistry Panel	X ^{c,n}	X ^c	X	X	X	X	X	X	X	X	X	
CBC, Differential, Platelets	X ^{c,n}	X ^c	X	X	X	X	X	X	X	X	X	
Coagulation	X ⁿ										X	
Serum Virology (HIV, HBV, HCV) ^k	X ⁿ											
Adverse Events		X	X	X	X	X	X	X	X	X	X	
Exploratory Immune Analysis		X		X	X		X				X	
Telephone Follow Up												X

^a Informed consent may be obtained on D0 after eligibility is confirmed and other screening protocols may be used to obtain screening labs and procedures as per NCI's internal SOP

^b Height will only be assessed at screening.

^c If the assessment is performed within 24 hours prior to the first dosing, a second assessment at baseline/week 0 can be omitted.

^d Complete medical history will be evaluated at screening and includes current and past cardiac and pulmonary history, documentation of diagnosis including history of current and prior cancers, prior treatment(s), and prior radiologic studies. Any new events in the medical history will be evaluated at baseline..

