8.4.4 Safety Analysis

DLTs will be evaluated continuously in a dose level. An overall assessment of whether to de-escalate to the next dose level will be made at least 1 week after the last subject in the previous dose level has received their first injection. A dose level will be considered safe if $< 33\%$ of subjects treated at a dose level experience a DLT (i.e., 0 of 3, ≤ 1 of 6, ≤ 2 of 9, ≤ 3 of 10). Safety will be evaluated in 3 or 6 subjects at each dose level in the dose escalation component of the study. Safety will continue to be monitored among additional subjects treated at the MTD or HTD in the dose expansion component of the study. A subject will be considered evaluable for safety if treated with at least one injection. DLTs will be observed for 1 week.

Safety endpoints will be analyzed as summary statistics during treatment and/or as change scores from baseline assessments. AEs will be coded as defined in the Medical Dictionary for Regulatory Activities (MedDRA). All AEs will be recorded and tabulated following each treatment (vaccine injection). AEs will be recorded by severity, frequency, and relationship to the study intervention and will be presented by System Organ Class (SOC) designations and preferred term groupings. Information on each AE will include start date, stop date, severity, relationship, expectedness, outcome, and duration. Adverse events leading to premature discontinuation from the study intervention and serious treatment-emergent AEs will be presented either in a Table or a Listing.

In addition, overall safety will be assessed by descriptive analyses using tabulated frequencies of AEs by grade using CTCAE Version 5.0 within dose levels and for the overall study population in terms of treatment-emergent AEs, SAEs, and clinically significant changes in safety laboratory tests, physical examinations, ECGs, and vital signs.

The safety events listed in section [8.4.6.2](#) will trigger a temporary suspension of the study injections.:

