13.2 APPENDIX B: INJECTION SITE REACTIONS DIARY CARD

Please answer all questions below once per day for the first 7 days

		Day 0 (Day of Injection)	Day +1	Day +2	Day +3	Day +4	Day +5	Day +6
1. Is there redness at the injection site?	Circle: Yes / No If yes measure longest diameter in millimeters (mm)	Yes / No _____mm						
2. Is there firmness or swelling at the injection site?	Circle: Yes / No If yes measure longest diameter in millimeters (mm)	Yes / No _____mm						
3. Is there soreness at the injection site?	Circle: Yes / No If yes tell us if the soreness is mild, moderate, or severe	Yes / No Mild Moderate Severe						
4. Have you experienced pain at the injection site?	Circle: Yes / No If yes tell us if the pain is mild, moderate, or severe	Yes / No Mild Moderate Severe						
5. Have you taken any medication for	Circle: Yes / No Provide name and	Yes / No Name: _____						

		Day 0 (Day of Injection)	Day +1	Day +2	Day +3	Day +4	Day +5	Day +6
injection site pain?	dose of medication	Dose: _____						
6. Have you experienced chills?	Circle: Yes / No If yes tell us if the chills are mild, moderate, or severe	Yes / No Mild Moderate Severe						
7. Record your daily temperature (Do not drink anything within 5 minutes prior to taking your temperature)	Circle: Yes / No If your temperature is 104°F for more than 24 hours, call your study doctor	Record Temp: _____

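### No staff contact is scheduled between dosing day and week 3 of the DLT period, so several of the 24-hour DLT exemptions cannot be reliably verified

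*Combined protocol and SAP*

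**What the plan says.** **Window.** Section 3.1.1 states: "For purposes of dose escalation the DLT evaluation period will be for 3 weeks following the first dose of drug". Section 8.4.4 states: "DLTs will be observed for 1 week". It also allows the de-escalation assessment from 1 week after the last subject's first injection.

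**Definition.** Any possibly vaccine-related toxicity of Grade 3 or higher is a DLT, "with the exception of transient (≤ 24 hours) Grade 3 flu-like symptoms or fever, which is controlled with medical management". A second exemption covers "transient (≤ 24 hours) Grade 3 fatigue, skin reactions or rash, headache, nausea, emesis that resolves to Grade ≤ 1".

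**Monitoring.** Section 3.1.2 says that "there will be a minimum of 3 days between enrolling successive subjects. DLTs will be monitored continuously". On dosing day, section 3.2 requires: "For the first injection, vital signs must be assessed 30 and 60 minutes after the injection". Section 3.6 adds a staff check of the injection site before discharge, with no stated time. In the section 3.5 calendar the next column after week 0 is week 3. The only telephone row is ticked under post-therapy follow-up.

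**Interim record.** Under section 3.6 and Appendix B, subjects fill in a card once a day from Day 0 to Day +6. It asks for redness and swelling in millimetres; soreness, pain and chills by severity; medication for injection site pain; and "Record your daily temperature". It tells subjects to phone if a temperature of 104°F lasts more than 24 hours. Staff go through the card at the next clinic visit, which is week 3.

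**The concern.** The dose decision rests on a count of DLTs in at most six subjects per level, in the first human use of this combination (section 1.2.8). The protocol promises continuous monitoring, but its schedule gives staff no planned information on a subject for about three weeks after the first dose. Several common Grade 3 symptoms count or do not count according to whether they lasted more than 24 hours, and the schedule provides no instrument that records this for most of them.

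At stake is the accuracy of that count. A non-serious Grade 3 event that has resolved by week 3 may go unreported. If it is reported, its duration may have to be reconstructed from memory.

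**Working it through.** **Sample size.** The plan's total reproduces: 2 × 6 (two dose levels) + 4 (expansion) + 16 (screen failures) = 32 (section 8.2). The point does not depend on it. The subjects concerned are the 6 to 12 in dose finding.

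**Coverage of the window.** Staff contacts scheduled between dosing day and week 3: 0. The card covers 7 of the 21 days in section 3.1.1, leaving 21 − 7 = 14 days with no scheduled capture before the visit. Under the 1-week observation of section 8.4.4, the card would cover 7 of 7 days.

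**Exempted items against card fields.**

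| Item with a 24-hour limit (3.1.1) | Field on the card (Appendix B) |
|---|---|
| Fever | One temperature a day; instruction to phone for sustained high fever |
| Flu-like symptoms | Chills and temperature only |
| Skin reactions or rash | Redness and swelling at the injection site only |
| Fatigue | None |
| Headache | None |
| Nausea | None |
| Emesis | None |

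Four of the seven have no field, and rash away from the injection site has none either. The card has no start or stop times. Local reactions are recorded in millimetres or as mild, moderate or severe, not by CTCAE grade.

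**What dates can settle.** Section 8.4.4 requires start date, stop date and duration for each adverse event, without giving a unit for duration. If start and stop fall on the same date, the event lasted at most 24 hours. If they are two or more dates apart, it lasted more than 24 hours. If they fall on consecutive dates, it may have lasted anything from minutes to nearly 48 hours, so dates alone cannot place it on either side of the limit.

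**Timeline at the minimum spacing.** This assumes that enrolment and dosing coincide and that every subject follows at exactly 3 days.
- First doses: days 0, 3, 6, 9, 12, 15.
- Planned week 3 visits (+21): days 21, 24, 27, 30, 33, 36.
- All six subjects are dosed before day 21. If the first subject's visit is brought forward to day 14 under the 1-week window in section 3.3, five of six are dosed before it.
- Earliest assessment under section 8.4.4: 15 + 7 = day 22. By then 1 of 6 has reached the planned week 3 visit, or 3 of 6 if every visit is 7 days early.

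**Sensitivity of the decision.** A level passes with at most 1 DLT in 6. With counted DLT rate q, P(pass) = (1 − q)^6 + 6q(1 − q)^5. The look at the first 3 does not alter this, because 2 of 3 already implies at least 2 of 6. The documents give no detection rate, so s below is an assumed share of DLTs detected, with q = p × s and a true rate p = 0.33:
- s = 1: 0.0905 + 0.2673 = 35.8%
- s = 0.90: 42.7%
- s = 0.75 (q = 0.2475): 0.1816 + 0.3583 = 54.0%
- s = 0.50: 74.1%

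The opposite error is also possible. If exempt events of unproven duration were counted, and this raised the counted rate from an assumed 20% to 33%, the chance of passing would fall from 65.5% to 35.8%.

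**The case against.** The strongest reply is that the protocol has more safety capture than the calendar suggests. The card is filled in daily during week 1 and carries a fever call instruction. Adverse events, chemistry and blood counts are assessed at week 3. Serious adverse events in the first 30 days go to the sponsor within 1 business day (section 7.3). The team meets weekly to discuss each patient (section 7.6.1), and cumulative halting rules apply (section 8.4.6.2). All of this stands, and it rules out several stronger readings.

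- *The DLT period is unobserved.* It is not, for the reasons above. What lacks a scheduled route is the non-serious Grade 3 event that resolves before week 3.
- *The exemptions cannot be judged, or no duration is recorded.* Section 8.4.4 requires dates and duration, and the card gives daily entries for fever, chills and local reactions. The weakness is coarse resolution and reliance on recall for the symptoms without a field.
- *The error always favours calling the dose safe.* Missed events do. But section 3.1.1 counts a qualifying event unless the exemption is met, so one whose short duration cannot be shown could equally be counted.
- *The 3-day spacing is useless.* A hospitalisation or other serious reaction could surface within the gap. The spacing only lacks a scheduled look at the preceding subject.
- *Six subjects will be dosed by day 15.* This is the worst case. Section 3.1.2 spaces enrolment rather than injections, a pause after the first 3 may be intended, and section 8.1 expects only that the MTD is found within a year.
- *Extra blood draws or ECGs are required.* The calendar gaps exist, but under section 6.1 a silent laboratory value might not be recorded as an adverse event even if drawn, and ECG timing has no bearing on the 24-hour limits.

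The weekly meeting does not answer the remaining point. It is not a subject contact, and no scheduled data from this interval reach it.

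**Conclusion.** The point holds in limited form. Continuous DLT monitoring is stated without a mechanism. No staff contact is scheduled between dosing day and week 3. Four of the seven symptom types with a 24-hour limit, and generalized rash, have no field on the only interim record. Several exemptions therefore cannot be reliably verified, and non-serious Grade 3 events may be missed or misclassified in either direction.

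The schedule facts come directly from the documents. The size of the effect does not: the pass probabilities rest on assumed detection shares and DLT rates, and the day 15 timeline rests on the fastest permitted accrual. What is certain is that a single event changes the decision at six subjects. This is a worthwhile, inexpensive improvement and does not invalidate the design. How much of the window the card covers depends on whether the period is 3 weeks or 1 week, and the documents contradict themselves on that.

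**What to change.** For dose-finding subjects:

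1. Add fatigue, headache, nausea, vomiting, rash away from the injection site, and start and stop times to the Appendix B card.
2. Record onset and resolution date and time for every Grade 3 or higher event in the DLT period.
3. Add brief, documented telephone adverse event contacts to the calendar: one within the first days after dose 1, then weekly to the end of the DLT period. State that these are the mechanism behind the continuous monitoring in section 3.1.2. They also give the weekly team meeting data to review.

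The sponsor should also reconcile the DLT period in section 3.1.1 with the observation period and decision timing in section 8.4.4.

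The cost is a few calls for each of 6 to 12 subjects, made by the existing team, and one card revision. No dose, treatment rule, clinic visit or blood sample changes.
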